2.5.2. Sample size

The decision to proceed to the full scale trial will be based on a futility design analysis, which guided our sample size estimates. We will determine this study as futile if we cannot produce a clinically significant weight loss in a significant proportion of participants. A clinically significant weight loss is set at 5% (which is the amount of weight that appears to be necessary to improve asthma control based on previous studies, and also the amount of weight loss required for FDA approval of a weight loss medication). A significant proportion of the population is set at 35% (FDA recommend that a weight loss medication must produce a 5% weight loss in 35% of participants to be considered effective).³¹

A straightforward way to test for futility with a binary outcome is based on the binomial distribution³². For a given minimum sufficient efficacy (p_1) and level that would indicate the intervention was ineffective (p_0), the threshold for continuing, c , can be determined for any sample size, n , as follows: the largest value of c such that $P(X \geq c | p_0) \leq \alpha$, type I error, and $P(X \geq c | p_1) \geq 1-\beta$, power, i.e. minimize the type II error. Ineffective thresholds of 5% and 10% were considered (Table 2). To be conservative, drop-outs will count as weight loss failures. With 40 patients, we have 94% power and $\alpha < 0.001$ using a threshold of 9 and assuming $p_0 = 0.1$ vs $p_1 = 0.35$, i.e. if ≥ 9 individuals have clinically significant weight loss we would reject futility and continue on to a larger trial. For the 12 Hispanics, we would need ≥ 3 ($\alpha = 0.026$, $1-\beta = 0.87$) and ≥ 2 ($\alpha = 0.02$, $1-\beta = 0.85$) individuals to achieve 5% weight loss reject futility assuming $p_0 = 0.1$ vs $p_1 = 0.45$ and $p_0 = 0.05$ vs $p_1 = 0.35$, respectively.

Table 2: Power, type I error, and threshold for rejecting futility for a variety of futility, p_0 , and minimum efficacy, p_1 , thresholds

p_0	p_1	c	$N = 40$	p_0	p_1	c	$N = 12$
			$\alpha, 1-\beta$				$C, \alpha, 1-\beta$
0.1	0.25	6	0.013, 0.96	0.10	0.40	2	0.11, 0.92
		7	0.003, 0.90			3	0.026, 0.77
		8	< 0.001, 0.82			4	0.004, 0.56
	0.30	7	< 0.001, 0.94		0.45	2	0.11, 0.96
		8	< 0.001, 0.89			3	0.026, 0.87
		9	< 0.001, 0.80			4	0.004, 0.70
	0.35	9	< 0.001, 0.94	0.05	0.35	1	0.12, 0.96
		10	< 0.001, 0.88			2	0.020, 0.85
		11	< 0.001, 0.79			3	0.002, 0.65

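### The two futility rules for the 12 Hispanic participants are not set at the trial's own 10% vs 35%, disagree at 2 responders, and print error rates that n = 12 cannot deliver at 10% vs 35%

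*Combined protocol and SAP*

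**What the plan says.** All of this is in Section 2.5.2 (Sample size) and its Table 2.

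- **Benchmark.** "A significant proportion of the population is set at 35"%, where response means a 5% weight loss.
- **Whole-cohort rule, n = 40.** The trial continues on 9 or more responders, "assuming $p_0 = 0.1$ vs $p_1 = 0.35$, i.e. if ≥ 9 individuals have clinically significant weight loss".
- **Nulls.** "Ineffective thresholds of 5% and 10% were considered (Table 2").
- **Hispanic participants, n = 12.** "For the 12 Hispanics, we would need ≥ 3 ($\alpha = 0.026$, $1-\beta = 0.87$) and ≥ 2 ($\alpha = 0.02$, $1-\beta = 0.85"). The first rule is for "individuals to achieve 5% weight loss reject futility assuming $p_0 = 0.1$ vs $p_1 = 0.45"; the second is for "p_0 = 0.05$ vs $p_1 = 0.35$, respectively".
- **Dropouts.** "drop-outs will count as weight loss failures", so the denominator stays at 12.

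The N = 12 half of Table 2 covers 0.10 vs 0.40, 0.10 vs 0.45 and 0.05 vs 0.35. It has no row for 0.10 vs 0.35.

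**The concern.** The pair of hypotheses that drives the main decision is the one pair not shown for the subgroup. One subgroup rule keeps the 10% null but raises the efficacy bar to 45%. The other keeps the 35% bar but halves the null to 5%. No reason is given why this group should need 45%, and nothing says which rule applies.

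The text speaks of rejecting futility for this group, with thresholds, alpha and power, in the same terms as for the full sample. Section 3.7 says that success would be evidence with an emphasis on minorities. A reader could take a subgroup verdict as comparable in strength with the n = 40 decision, and two rules that can disagree leave room to choose between them after the data are seen.

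**Working it through.** **Inputs.** n = 12; thresholds 3 and 2; p0 = 0.10 or 0.05; p1 = 0.45 or 0.35 (all from Section 2.5.2). The stated method is "the largest value of c such that $P(X \geq c | p_0) \leq \alpha$, type I error, and $P(X \geq c | p_1) \geq 1-\beta$, power". So alpha = P(X ≥ c | p0) and power = P(X ≥ c | p1), with X binomial(12, p).

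**Step 1: the plan's own figures.**

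| Rule and hypotheses | Printed alpha, power | Exact, as written | Exact, one responder higher |
|---|---|---|---|
| ≥ 3, 0.10 vs 0.45 | 0.026, 0.87 | 0.111, 0.958 | ≥ 4: 0.026, 0.866 |
| ≥ 2, 0.05 vs 0.35 | 0.02, 0.85 | 0.118, 0.958 | ≥ 3: 0.020, 0.849 |

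The printed values do not reproduce for the written rules. They match thresholds one higher than the text states.

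**Step 2: the missing row, 0.10 vs 0.35.** P(X = k) = C(12, k) p^k (1 − p)^(12 − k).

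- At p = 0.10, P(X = 0, 1, 2, 3) = 0.2824, 0.3766, 0.2301, 0.0852.
- At p = 0.35, P(X = 0, 1, 2, 3) = 0.0057, 0.0368, 0.1088, 0.1954.

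Subtracting the cumulative sums from 1 gives:

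| Threshold | alpha at 0.10 | Power at 0.35 | Missed at 0.35 |
|---|---|---|---|
| ≥ 2 | 0.341 | 0.958 | 4% |
| ≥ 3 | 0.111 | 0.849 | 15% |
| ≥ 4 | 0.026 | 0.653 | 35% |
| ≥ 5 | 0.004 | 0.417 | 58% |

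An alpha near the printed 0.026 comes with power 0.653. Power near the printed 0.85 comes with alpha 0.111. No threshold gives both. Taking 80% power as a yardstick (mine, not the plan's), no threshold reaches it with alpha ≤ 0.05, or even ≤ 0.10. The smallest n that has 80% power with alpha ≤ 0.05 is 18 (≥ 5: alpha 0.028, power 0.811).

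**Step 3: conflict between the rules.** With exactly 2 responders, the rule of at least 2 rejects futility and the rule of at least 3 does not. P(X = 2) is 0.341 − 0.111 = 0.230 at a true 10%, and 0.958 − 0.849 = 0.109 at a true 35%.

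**Step 4: comparison with the main rule.** At n = 40, ≥ 9, 0.10 vs 0.35, the exact values are alpha 0.0155 and power 0.970. The printed figures there (below 0.001 and 0.94) also do not reproduce, which is a separate matter. Even so, the main rule controls both errors in a way that no threshold at n = 12 can.

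**The case against.** Several points on the other side stand.

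- **Disclosure.** Both hypothesis pairs are printed beside the rules, and 5% is a declared null. Table 2 also shows that, at the printed alpha of 0.026, power falls from 0.87 at 45% to 0.77 at 40%. A reader might infer that the weakness was concealed. The documents do not support that: one row is absent and one choice is unexplained.
- **Power.** A reader might infer that both changes raise power. Only the move to 45% does so directly. At a fixed threshold, halving the null lowers alpha and leaves power unchanged (≥ 3 at 35%: 0.849 either way).
- **False futility.** A reader might infer that a programme meeting the 35% bar would be called futile 35% of the time rather than 13%. Those rates are 1 − 0.653 and 1 − 0.866, and both belong to ≥ 4, which the text never states as a subgroup rule. The written rules miss such a programme 15% or 4% of the time.
- **Benchmark.** The plan sets no target of 5% alpha and 80% power for this group.
- **Consequence.** The decision to proceed rests on the whole cohort. No action is attached to the subgroup verdict, and the two rules can be read as alternative planning scenarios.

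The last point limits the harm but does not remove the problem. If these are scenarios, the plan should say so. As it stands it gives two thresholds for one verdict, with error rates that do not apply at the trial's own hypotheses.

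**Conclusion.** The point holds as one about a subgroup claim; the go/no-go decision is not affected. The plan gives two rules for the same 12 people, neither set at 10% vs 35%, with no reason for 45% and no statement of which governs. They disagree with probability 0.23 at a true 10% and 0.11 at a true 35%. The printed combination of alpha 0.02 to 0.026 with power 0.85 to 0.87 cannot be had at 10% vs 35% with n = 12.

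Under the rules as written, the main risk is that an ineffective programme passes: 11% for at least 3 and 34% for at least 2, at a true 10%. The risk moves to false futility (35% at a true 35%) only if the threshold is raised to 4 to match the printed alpha of 0.026.

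These figures assume exactly 12 Hispanic participants, independent outcomes and dropouts counted as failures. A different number enrolled would change them.

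**What to change.** 1. Add an N = 12 row to Table 2 at 0.10 vs 0.35 with correct tails: ≥ 2, 0.341 and 0.958; ≥ 3, 0.111 and 0.849; ≥ 4, 0.026 and 0.653. Correct the existing N = 12 rows so that each threshold matches its alpha and power.
2. Replace the two subgroup rules with a descriptive report: count, proportion and exact 95% confidence interval. For example, 4 of 12 gives 9.9% to 65.1% (Clopper-Pearson). Section 2.5.3 already plans exact intervals for the proportion with 5% weight loss; it need only name this subgroup.
3. State that 12 participants do not support a separate futility verdict.

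The cost is a change of wording and one table row, with no added participants. The stated subgroup figures become less favourable, and the trial gives up a formal verdict for this group. If the sponsor wishes to keep a verdict, it should name one rule, justify its hypotheses and print the exact error rates at 10% vs 35% beside it.

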2.5.3. Statistical methods

Descriptive statistics will be generated for all study parameters (e.g. SD of change in ACT). Cross-sectional comparisons will be made using Kruskall-Wallis and Fisher's exact tests. We will determine the proportion of participants achieving a 5% weight loss with exact 95% confidence intervals. Mixed effects models will be used to analyze repeated measures.

3. Monitoring

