1.4. Overview of study design

This will be a pilot study of a weight loss intervention at two centers, the University of Arizona and the University of Vermont. The primary outcome of interest will be the percent of participants achieving a 5% weight loss, which is the amount of weight loss that prior studies suggest is required to improve asthma control.

This will be a single arm-phase II futility trial; the “futility” to be assessed is the ability to produce weight loss. Such designs are widely used in efficiently informing decisions to proceed to Phase III clinical trials. This trial design is appropriate when the effect of the placebo arm can reasonably be estimated (weight loss is likely to be close to 0), and the toxicity of the treatment is minimal (no toxicity is anticipated related to weight loss).¹⁸ Therefore, this will be a single arm 6-month study of 40 participants (20 at each site). All participants will be assigned to the weight loss intervention, which is described in detail below.

2. Methods

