2.4.1. Basic components of the weight loss program

This 6-month intervention will include restricted calorie intake and increased physical activity. Key behavioral strategies to facilitate changes in dietary habits and activity patterns will be introduced, promoted and reinforced throughout the program. Weekly "group meetings" in a synchronous chat (i.e., in real time) led by a facilitator will be the venue for the group process. Extensive web-based resources to support behavior changes will be offered. The online groups will be "closed" such that those individuals who start the group remain in that group for the duration of their participation. Group chat sessions will meet online weekly for 6 months.

1. *Diet*

A balanced reduced calorie deficit diet will be prescribed. All participants will be given an individualized calorie goal. Emphasis will be placed on consuming a diet high in fruits, vegetables, and whole grains, and low in fat, sugar, salt and alcohol. Participants are asked to target fat intake to 25% of their overall calorie goal because a number of studies ^{28,29} suggest superior weight loss when fat and calories are both controlled.

Participants will record their daily calorie and fat intake daily electronically. They will have access on the study website to calorie and fat gram guides which use pull down menus and personally customized calorie/fat counters to facilitate ease of recording. The interventionist will review these diaries weekly and provide feedback to reinforce or shape new behaviors.

2. *Exercise*

Participants will be provided with graded goals to reach the recommended weekly minimum of 200 minutes of moderate intensity exercise by week 9 of the program. We will recommend brisk walking as in our previous studies. At visit 1, we will verify they have a safe place to exercise as in our previous studies, other forms of aerobic exercise will also be encouraged should the participant prefer. All exercise will be monitored using electronic diaries that include pull down menus for a wide range of activities.

3. *Behavioral strategies*

The major features of the behavior modification strategies in the program are based on Social Cognitive Theory³⁰ and are described below. [name] and [name] will be involved in training the bilingual lifestyle coach in cultural adaptation for Hispanic participants.

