2.4.2. Internet delivery of behavioral weight control program

Participants will have access to behavioral lessons weekly. The standard version of the lesson is very visual, capitalizing on the capabilities of the internet delivery. We will be notified over the Web site when participants have completed lessons and we will, therefore, be able to electronically assess compliance with this program component

All potential participants will be given an orientation to the website and MyFitnessPal at Visit 1 prior to entering the weight loss program. We will assess compliance with asthma and food diary entries at Visit 2, only participants who have completed diary requirements (same 3 days of asthma and food diaries) will be considered eligible to continue in study.

Participants will be enrolled into a “group” at Visit 2, although they will not meet in-person and this “group” will be maintained throughout an individual’s study participation. Groups will be homogenous with respect to language (English or Spanish). Participants will have access to the Internet site and will be assigned a group on-line chat time. The group facilitator will e-mail them weekly, and they will be encouraged to use various components of the Web site. Individual usage of the site will be tracked by username through server activity logging and the use of WebTrends (NetIQ Corporation, San Jose, CA) log analysis software.

Participants will have access to new behavioral lessons each week. Participants will be provided with a computer. We will provide them with a data plan or hot-spot for internet access if they do not have internet access.

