2.4.6. Assembling weight control cohorts

The intervention requires that 5-10 participants form a group to participate in the weekly group chat sessions. A group may include participants from both sites. The group will essentially be a cohort of participants starting and ending the study at the same time. Because it is essential that the V1 and V2 visits be conducted close together, the cohorts need to be assembled prior to starting the study. Individuals who are interested in the study will be directed to the PLAN website to complete a study registrations form. The form will include individuals' names, contact information, basic eligibility information, information on the days of the week and times that a person will be consistently available for group chat sessions, preferred language (English or Spanish), and the center. These data may be collected prior to an individual providing consent for the study. The registration form will include text briefly describing study and how the information provided on the registration form will be used. Clinical center personnel will only be able to see the data from individuals who selected their center for attending study visits. The central coordinator will be able to view registration data from both sites in order to assemble the cohorts of 5-10 individuals who can participate in group chats at the same time. Once there are sufficient individuals who can participate in group chats at the same or similar times, the central coordinator will contact the clinical center coordinator to schedule V1 and V2 visits for these individuals. If the individual has not provided consent, consent will be obtained at the V1 visit before screening. Once all the cohort has completed V2, the coaches will contact cohort members to schedule the first chat. The goal is for the first chat session to take place in the 2 weeks following V2.

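### Should the 9-of-40 futility rule and the exact confidence interval allow for clustering by chat group?

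*Combined protocol and SAP*

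**What the plan says.** Section 1.4 sets a single-arm study of 40 participants, 20 per site. Section 2.4.6 states: "The intervention requires that 5-10 participants form a group to participate in the weekly group chat sessions". It adds: "The group will essentially be a cohort of participants starting and ending the study at the same time". Under section 2.4.1 the weekly real-time chats "led by a facilitator will be the venue for the group process", and the groups are closed, so members stay together throughout. Section 2.4.2 makes each group single-language, and section 2.4.6 lets a group span both sites.

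Section 2.5.2 derives the go rule from a single binomial count: "A straightforward way to test for futility with a binary outcome is based on the binomial distribution". The study continues if at least 9 of 40 reach 5% weight loss, and drop-outs count as failures. For the primary proportion, section 2.5.3 says: "We will determine the proportion of participants achieving a 5% weight loss with exact 95% confidence intervals". For longitudinal data it says only: "Mixed effects models will be used to analyze repeated measures". No section gives an ICC, a design effect or an interval adjusted for group.

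**The concern.** The plan relies on group process as part of the treatment, and group members share their sessions, calendar period and language. Positive correlation in outcome within a group is therefore plausible. If it exists, the number of responders out of 40 varies more than a binomial count. The true chance of passing the 9-of-40 rule with an ineffective programme would then exceed the binomial figure, and the exact interval could cover less than 95% of the time.

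At stake are the error rate of the decision to launch a larger trial, the stated precision of the primary estimate, and possibly a chance to learn the between-group spread for that trial. The analysis text does not say whether the mixed models would carry a group term.

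**Working it through.** **Inputs.** n = 40 (section 1.4); go if X ≥ 9, p0 = 0.10, p1 = 0.35 (section 2.5.2); groups of 5 to 10 (section 2.4.6), hence 40/10 = 4 to 40/5 = 8 groups. The ICC is an assumption, taken from 0 to 0.10.

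**Step 1: the plan's own figures.** For X ≥ 9 of 40, the exact binomial gives P(X ≥ 9 | 0.10) = 0.0155 and P(X ≥ 9 | 0.35) = 0.970. Section 2.5.2 states alpha below 0.001 and power 94%. That mismatch exists under independence. It is a separate matter and has nothing to do with chat groups, so the baseline used here is 0.0155 and 0.970.

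**Step 2: the rule and interval under clustering.** Responders within each group follow a beta-binomial distribution with the given ICC, summed over equal groups. The design effect is DE = 1 + (m − 1) × ICC; for example, 1 + 4 × 0.05 = 1.20 for groups of 5 and 1 + 9 × 0.05 = 1.45 for groups of 10. Ranges run over 8 groups of 5, 5 of 8 and 4 of 10.

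| Assumed ICC | False-go rate at 10% | Power at 35% | Exact CI coverage, true rate 22.5% | Exact CI coverage, averaged over 10% to 45% |
|---|---|---|---|---|
| 0 | 0.0155 | 0.970 | 0.965 | 0.968 |
| 0.01 | 0.018–0.020 | 0.964–0.967 | 0.957–0.961 | 0.959–0.964 |
| 0.02 | 0.020–0.025 | 0.958–0.965 | 0.948–0.958 | 0.951–0.960 |
| 0.05 | 0.026–0.039 | 0.940–0.957 | 0.921–0.946 | 0.924–0.949 |
| 0.10 | 0.036–0.060 | 0.911–0.943 | 0.874–0.926 | 0.878–0.929 |

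The false-go rate passes 0.05 only at ICC 0.10 with groups of 8 (0.051) or 10 (0.060).

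**Step 3: what an adjusted interval would show.** Use Clopper-Pearson limits at effective counts x/DE and 40/DE.

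- At the 35% target (14/40), the planned interval is 20.6% to 51.7%. At ICC 0.05 it becomes 19.4% to 53.4% (groups of 5) or 18.0% to 55.4% (groups of 10).
- At the boundary (9/40), the planned interval is 10.8% to 38.5%. At ICC 0.05 the lower limit is 9.9% (groups of 5) or 8.9% (groups of 10).

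**Step 4: is the adjusted interval better?** At a true ICC of 0.05, the planned interval averages 0.924 to 0.949 coverage, and the adjusted one averages 0.970 to 0.972. The first falls short by 0.001 to 0.026 and the second overshoots by 0.020 to 0.022. If the true ICC is 0 and 0.10 is assumed, the adjusted interval averages 0.990 (groups of 5) to 0.998 (groups of 10). A clear gain appears only around ICC 0.10.

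**Step 5: could the pilot estimate the ICC?** In 40,000 simulated normal data sets per layout, with true ICC 0.05 and the ANOVA estimator, the estimate is zero or negative in 40% to 42% of trials. Its central 95% range is about −0.10 to 0.30 (4 groups of 10) or −0.17 to 0.33 (8 groups of 5). With true ICC 0, the estimate is 0.10 or more in 11% (4 groups of 10) to 18% (8 groups of 5) of trials.

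**The case for a change.** The strongest contrary case is that the plan builds in dependence and then ignores it, that nothing in the documents shows the ICC to be small, and that a sensitivity interval costs a few lines and no new data. It has most force at exactly 9 of 40. There the reported interval just excludes the ineffective rate of 10%, and at ICC 0.05 it no longer would. Fixing the ICC values in advance would also prevent a convenient choice afterwards.

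Much of this stands. The independence assumption is unstated, and the 9/40 illustration is correct. But section 2.5.2 ties the decision to the count and not to a confidence limit, so a wider interval would not reverse a go. The documents support an ICC of 0.05 or more no better than 0.01. Several components are individual: calorie goals and diary feedback in section 2.4.1, and tailored adherence support in section 2.4.3.

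The mixed-model part is weaker. The plan's silence on random effects for secondary repeated measures is not a wrong rule. A random intercept for group would not capture correlation in weight change that arises only after treatment starts. Because groups are single-language, a group term would also mix group process with language.

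**Conclusion.** No change to the plan is needed. The alpha, power and exact interval do assume independent participants, and positive correlation within chat groups would make the first two somewhat optimistic and the interval somewhat narrow. Under an assumed ICC of 0.01 to 0.10 with equal groups of 5 to 10, the false-go rate is about 0.018 to 0.060 and power stays at about 0.91 or more. Coverage falls clearly below nominal only at ICC 0.05 with groups of 8 to 10, or at 0.10.

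The 9-of-40 decision is the same with or without an adjusted interval. The adjusted interval is not clearly better below an ICC of about 0.10, and an ICC estimated from 4 to 8 groups would be close to uninformative and could mislead planning of the later trial. For a 40-person pilot the simple binomial analysis is a fair trade-off. Analysts may mention the independence assumption, or add an interval at a pre-set ICC when reporting, but a reasonable statistician could decline both. The conclusion rests on the assumed ICC range; an ICC well above 0.10 would weaken it.
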